4.1.1.3 Handling of Dropouts or Missing Data

4.1.1.3.1 Missing Efficacy Endpoint Data

While all possible efforts will be made to ensure that participants stay in the study and all data is collected as scheduled, the occurrence of missing data cannot be eliminated.

Participants who sign the informed consent form but do not receive the study intervention may be replaced. Should there be a participant(s) who signs the informed consent form, and receives the study intervention and subsequently withdraws, or is withdrawn or discontinued from the study before the Day 180 Visit, an additional participant(s) in the same age group may be enrolled to ensure that an adequate number of participants complete the Day 180 visit assessments.

No other imputation will be used in the study except for partial dates described in Section [4.1.1.7](#).

4.1.1.4 Handling of Rescreened Participants

Rescreening of participants is allowed with approval of the Sponsor. If a patient initially screen fails and is subsequently enrolled then that participant will have two subject IDs within the EDC system (one ID XXX-XXXXA for the screen failure and associated data collection, and one ID XXX-XXXXB for the subsequently enrolled participant).

4.1.1.5 Analysis Visit Windows

By-visit summaries will be based on electronic case report form (eCRF)-defined nominal visits.

In general, analysis of all variables for this study will use the nominal visit or time point as collected on the electronic case report form (eCRF) and/or database. Scheduled visits will be selected over unscheduled visits.

For those participants who discontinue early from the study and the Early Termination (ET) visit satisfies the following condition:

- 20 days ≤ the date of ET - the date of the last visit before ET + 1 ≤ 40 days

then the ET visit will be mapped to the next scheduled visit. Otherwise, the ET will not be mapped into any analysis visits.

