### 1.3. Schedule of Activities

**Table 1: Schedule of Activities**

Study Day (window)	Screening	Treatment									EOS	ET
	-35 a to -1	1 b	2	15	30 (±2)	45	60 (±3)	90 (±3)	120 (±5)	150 (±5)	180 (±5)	-
At-clinic visit	X	X			X			X			X	
At-home telehealth visit c			X				X		X	X		
Telephone Contact d				X		X						
Procedure/Assessment												
Study intervention administration e		X			X		X	X	X	X		
Informed consent f	X											
Inclusion/exclusion criteria g	X	X										
Demographic/baseline characteristics	X											
Medical history	X											
PH disease history h	X											
Medication history i	X											
PH genotyping j	X											
Plasma oxalate sample	X										X	X
Spot urine collection k	X				X		X	X	X	X	X	X
Plasma PK sample l		X	X		X			X		X		X
Record fluid intake m	X				X		X	X	X	X	X	X
12-lead ECG n	X	X			X			X			X	X
Vital signs o	X	X	X		X		X	X	X	X	X	X
Physical examination p	X	X	X		X		X	X	X	X	X	X
Height and body weight q	X	X			X			X			X	X
Hematology r	X	X			X			X			X	X
Chemistry r	X	X			X		X	X	X	X	X	X
Coagulation s	X	X			X			X			X	X
eGFR t	X	X			X		X	X	X	X	X	X
Urinalysis u	X	X			X		X	X	X	X	X	X
Urine pregnancy test (WOCBP) v	X	X			X		X	X	X	X	X	X
Record stone events w		X	X		X		X	X	X	X	X	X
Kidney ultrasound x	X										X	X
Echocardiogram y	X										X	X
ADA sample	X				X			X		X	X	X

Study Day (window)	Screening	Treatment									EOS	ET
	-35 a to -1	1 b	2	15	30 (±2)	45	60 (±3)	90 (±3)	120 (±5)	150 (±5)	180 (±5)	-
At-clinic visit	X	X			X			X			X	
At-home telehealth visit c			X				X		X	X		
Telephone Contact d				X		X						
Procedure/Assessment												
Pediatric burden assessment z		X			X		X	X	X	X	X	X
PedsQL aa	X										X	X
Pharmacoeconomics bb	X							X			X	X
Record AEs and SAEs cc	X	X	X	X	X	X	X	X	X	X	X	X
Concomitant medications i		X	X		X		X	X	X	X	X	X

a An extra 14-day period will also be granted for participants who are required to repeat initially unanalyzable screening laboratory assessment samples or where lab samples are delayed due to technical/logistical issues at the central lab.

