b In order to minimize blood loss in participants, samples to be drawn for screening should be collected not less than 28 days prior to samples drawn on Day 1.

c Visits for Days 2, 60, 120, and 150 may be conducted at the clinic or as at-home telehealth visits. During at-home telehealth visits, home-health nurses will collect the required blood and urine samples and perform an assessment of vital signs. The Investigator will contact the participant's caregiver via telephone and/or video conference to assess the general well-being of the participant and determine if any adverse events have occurred. The Investigator must affirm that nedosiran may be administered prior to administration.

d The Investigator will contact the participant's caregiver via telephone and/or video conference to assess the general well-being of the participant and determine if any adverse events have occurred.

e After the first 2 injections of nedosiran, visiting nurses or caregivers will administer SC injections at home for those months at which a study-site visit is not required. The total dose will be based upon body weight recorded on study Day 1. For participants < 6 months of age at Screening, the dose will be adjusted at Day 90 to capture changes in weight; no other dose adjustments are allowed.

f Parental informed consent (and minor assent, if applicable per local regulations) is required prior to initiation of screening procedures.

g Participant eligibility (with the exception of clinical laboratory testing) will be re-confirmed prior to administration of study intervention on Day 1.

h PH history to include 12-month history of stone events, or as applicable for those less than 12 months of age (Section 8.1.3).

i To include vitamin B6 (pyridoxine), if applicable.

j Participants without documented genotyping must provide a DNA sample for testing. For participants who weigh ≤ 11 kg, PH genotyping will be performed via buccal swab; for all other participants, while genotyping via buccal swab is recommended to reduce blood sample volumes, genotyping performed via whole blood sample is allowed.

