k Spot urine samples will be collected for the determination of Uox and urinary creatinine. At screening, 6 spot urine samples (3 of which must be second morning voids) will be collected over a 3-day period. On-treatment, 4 spot urine samples (2 of which must be second morning voids) will be collected over a 2-day period on a monthly basis.

 Plasma sampling times for PK analysis (see Section 8.5):

Sampling times:	Allowable Windows:
Day 1: one sample in the 0- to 4-hour postdose window and one sample in the 4- to 24-hour postdose window	Predose: within 30 minutes before administration of study intervention
Days 2, 30, and 90: one single sample during the visit	Not applicable for other samples
Day 150: predose, one sample in the 0- to 4-hour postdose window, and one sample in the 4- to 24-hour postdose window	

A single plasma sample should be collected at the final visit from participants who discontinue study intervention or are withdrawn from the study. When multiple assessments are due at the same time point, PK sampling should be performed at the nominal time point, with the preferred order of assessments ECG, vital signs, PK, and then other assessments.

- m Participants should maintain consistent fluid intake (i.e., hyperhydration) over the course of the study (Section 5.3). Participants' caregivers will report daily fluid intake over the week prior to each urine collection period (Section 8.1.5). Recording of fluid intake only applies to non-breastfed participants.
- n On Days 1 and 30, ECG to be performed predose and at 6 hours postdose. A single ECG to be performed at other visits, as indicated (Section 8.2.4). A  $\pm$  30-minute window is allowed if multiple assessments are due at the same time point.
- o Vital signs on Day 1 and Day 30 to be assessed predose and at 6 hours postdose (Section 8.2.3). A  $\pm$  30-minute window is allowed if multiple assessments are due at the same time point. In such cases, PK sampling should be performed, preferably at the nominal time point, with the preferred order of assessments ECG, vitals, PK, and then other assessments.

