1.1.2 Primary Estimand

The primary clinical question of interest is: What is the treatment effect of nedosiran in lowering urinary oxalate excretion (Uox) assessed via percent change from baseline in spot urinary oxalate-to-creatinine ratio at Month 6 in PH1 pediatric participants (birth to 11 years of age) with relatively intact renal function.

For the primary objective, the estimand is defined with five attributes:

- Treatment condition of interest is the monthly nedosiran administration.
- The target population is PH1 pediatric participants (birth to 11 years of age) with relatively intact renal function.
- The endpoint is percent change from baseline at Month 6 in spot urinary oxalate-to-creatinine ratio.
- The intercurrent events (ICEs) include treatment discontinuation for any reasons and will be handled by the treatment policy strategy.

[figure not shown]
Population-level summary is the percent change from baseline at Month 6 estimated by Mixed-effect Model Repeated Measures (MMRM) approach.

Rationale for estimand: The primary estimand assesses the treatment benefit of nedosiran in lowering urinary oxalate-to-creatinine ratio that can be expected in clinical practice, provided that the treatment adherence in the study reflects what would be seen in clinical practice.

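### Early-termination urine is mapped by the gap since the last visit, not by study day, so a withdrawing child who missed the preceding monthly visit loses a sample taken in a planned visit window

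*SAP*

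**What the plan says.** SAP 4.1.1.5 analyses data by nominal eCRF visit and adds one special rule for withdrawals. It opens "For those participants who discontinue early from the study and the Early Termination (ET) visit satisfies the following condition", the condition being "20 days ≤ the date of ET - the date of the last visit before ET + 1 ≤ 40 days". When the condition is met, "then the ET visit will be mapped to the next scheduled visit. Otherwise, the ET will not be mapped into any analysis visits". The section does not define *visit*. It also does not say whether *next* counts from the last visit or from the ET date.

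The Schedule of Activities (Protocol 1.3, Table 1) has separate columns for the Day 180 end-of-study visit (EOS) and for ET, with spot urine in both. On the urine schedule its footnote says: "On-treatment, 4 spot urine samples (2 of which must be second morning voids) will be collected over a 2-day period on a monthly basis". The marked days are 30, 60, 90, 120, 150 and 180. Day 2 has no spot urine but is a visit: "Visits for Days 2, 60, 120, and 150 may be conducted at the clinic or as at-home telehealth visits". Days 15 and 45 sit in a row of their own, "Telephone Contact", also without urine.

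The primary model (SAP 4.2.2) takes percent change at the scheduled visits from Month 1 to Month 6. SAP 4.1.1.3.1 allows no imputation of missing efficacy values.

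**The concern.** An ET urine collection is an observed efficacy value with a known study day. The rule keeps or discards it according to whether the child attended the visit before it. Two withdrawing children sampled on the same study day can thus be treated differently: one contributes to that month and the other contributes nothing there.

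At stake is the last observed value from a child who leaves. An unmapped value is treated as missing in the model, although it exists in the database. In a single-arm study planned for about 20 completers, each value carries some weight. A data-handling rule should not make availability depend on earlier attendance when the sample date would settle the matter.

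There is also a gap in the wording. Day 2 is a scheduled visit without urine, so a literal reading of *next scheduled visit* can point to a visit at which the endpoint is not measured.

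**Working it through.** **Inputs.** From SAP 4.1.1.5: count = ET date - last visit date + 1, mapped if 20 to 40. From Protocol Table 1: Day 30 ±2, Days 60 and 90 ±3, Days 120, 150 and 180 ±5, and no window shown for Days 1 and 2. Telephone contacts are not counted as visits here.

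**Step 1: does the rule work when no visit is missed?** For Month 6 the last visit falls on Days 145 to 155 and ET on Days 175 to 185.
- Smallest count: 175 - 155 + 1 = 21.
- Largest count: 185 - 145 + 1 = 41.
- Of the 11 × 11 = 121 date pairs, 120 satisfy the rule. Only Day 145 with Day 185 (41) fails.

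The same check gives 5/5, 35/35, 49/49, 77/77 and 120/121 at Months 1 to 5. The limits of 20 and 40 therefore suit consecutive monthly visits.

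**Step 2: the preceding monthly visit is missed.**

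| ET in window of | Last visit attended | Smallest count | Largest count | Pairs mapped |
|---|---|---|---|---|
| Month 2 (57–63) | Day 2 | 57 - 2 + 1 = 56 | 63 - 2 + 1 = 62 | 0 of 7 |
| Month 3 (87–93) | Days 28–32 | 87 - 32 + 1 = 56 | 93 - 28 + 1 = 66 | 0 of 35 |
| Month 4 (115–125) | Days 57–63 | 115 - 63 + 1 = 53 | 125 - 57 + 1 = 69 | 0 of 77 |
| Month 5 (145–155) | Days 87–93 | 145 - 93 + 1 = 53 | 155 - 87 + 1 = 69 | 0 of 77 |
| Month 6 (175–185) | Days 115–125 | 175 - 125 + 1 = 51 | 185 - 115 + 1 = 71 | 0 of 121 |

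Every count exceeds 40, so none of these samples is ever mapped.

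**Step 3: same sample day, different history.** Take ET on Day 178.
- Last visit Day 150: 178 - 150 + 1 = 29, mapped to Month 6.
- Last visit Day 120, Day 150 missed: 178 - 120 + 1 = 59, not mapped.

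**Step 4: Day 2 missed.** With a last visit on Day 1, the condition 20 ≤ ET - 1 + 1 ≤ 40 is met for ET on Days 20 to 40. If *next* counts from the last visit, the target is Day 2, which has no spot urine and is not a Month 1 to 6 visit. If *next* counts from the ET date, this does not arise.

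**Step 5: assignment by study day.** With targets at Days 30, 60, 90, 120, 150 and 180, all 11 days from 175 to 185 go to Month 6 whether or not Day 150 was attended. Days 2, 15 and 45 are never targets.

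**The case against.** The strongest reply is that the rule does its evident job. For a child who attends every month and then withdraws, almost every on-time ET sample is mapped (Step 1). The study is descriptive, few children are likely to be affected, and a child's earlier visits stay in the model when the ET value is lost. All of that stands. It limits the size of the problem but does not explain why attendance, and not the sample date, should decide.

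A second reply is that nearest-visit assignment labels some samples loosely: Day 166 would become Month 6, well outside Day 180 ±5. That is true, but the present rule already does the same. With a last visit on Day 145, ET on Day 164 gives 164 - 145 + 1 = 20 and is mapped to Month 6.

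Three stronger readings are tempting, and the documents do not support them.
- **Any child who misses Day 150 loses Month 6.** A reader might infer this, but the rule covers only early withdrawal from the study. A child who misses Day 150 and attends Day 180 is recorded at EOS and analysed at nominal Month 6.
- **The rule defeats the treatment-policy estimand.** SAP 1.1.2 says the intercurrent events include "treatment discontinuation for any reasons and will be handled by the treatment policy strategy". Protocol 7.1.1 separates stopping treatment from leaving the study, and children who only stop treatment continue with the scheduled visits. Their values never meet the ET rule.
- **ET urine is sent to telephone contacts.** Table 1 lists Days 15 and 45 apart from both visit rows, so on the ordinary reading nothing is mapped there. The possibility arises only because *visit* is undefined.

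**Conclusion.** The concern holds in a limited form. For a child who withdraws from the study after missing the preceding monthly visit, ET urine collected in a planned window at Months 2 to 6 is never mapped and is lost to the primary model. A sample on the same study day from a child who attended that visit is, with rare edge exceptions, kept. Mapping to Day 2 is a lesser fault that depends on how *next* is read.

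The result assumes that the visit is recorded as ET, that telephone contacts are not visits, and that the windows are those in Table 1. EOS visits and children who stop treatment but stay in the study are unaffected.

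The number of values involved cannot be derived. The documents give no withdrawal or missed-visit rate. A reader might infer one from the 25 and 20 participants planned, but the protocol synopsis speaks of 25 enrolled, whereas Protocol 4.1 and 9.2 and SAP section 5 speak of 25 screened, so the difference may include screen failures. The number is probably small, and no bias of any stated size is claimed. This is an inexpensive improvement to the plan, not a threat to the study's conclusions.

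**What to change.** In SAP 4.1.1.5, replace the gap rule for spot urine with assignment by study day:
- Map the ET sample to the nearest planned urine visit (Days 30, 60, 90, 120, 150 or 180) when that visit has no scheduled value.
- Pre-specify the window limits, including the earliest day accepted for Month 1 and how a sample exactly midway between two visits is assigned.
- State that Day 2 and the telephone contacts are not mapping targets.

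The cost is a short SAP edit and a small programming change, with no new data or visits. The downside is that some ET samples taken outside the protocol visit windows will carry the label of the nearest month. A listing of the actual study day for every mapped ET sample would make this visible.

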4.1.1.6 Derived Variables

- Change from baseline = value at current time point – baseline value
- Percentage change from baseline = $\left(\frac{\text{value at current time point} - \text{baseline value}}{\text{baseline value}} \right) * 100\%$
- Spot urinary oxalate-to-creatinine ratio = the average of all the spot urinary oxalate-to-creatinine ratio collected at the specific visit.
- Treatment-emergent AE (TEAE) = any AE with an onset date/time on or after administration (including any partial administration) of the first dose of study intervention and until the study completion date from the end of study CRF.
- Body surface area will be calculated using the following formula (DuBois & DuBois, 1916):
$$BSA = (\text{Weight}^{0.425} \times \text{Height}^{0.725}) \times 0.007184;$$
 with weight in kilograms and height in centimeters.
- Body mass index (BMI) will be calculated using the formula: $\text{Weight [kg]} / (\text{Height}^2 [\text{m}^2])$.
- Estimated Glomerular Filtration Rate (eGFR) will be calculated as described in Protocol Section 8.2.6.1.
- Annualized stone event rate will be derived as number of stone events in the exposure period / total number of years exposed.

The number of stone events will be calculated as the number of discrete (non-concurrent) adverse events marked as a Kidney Stone Event on the adverse event CRF. Kidney stone events include renal stone requiring medical intervention, stone passage with or without hematuria, and renal colic requiring medication.

Concurrent events will be defined as events occurring within the same 4-week (28-day) window. For example, renal colic treated with medication on Monday 12 November 2019 followed by stone passage without hematuria on Friday 30 November 2019 is a single (concurrent) stone event (18 days between start and stop of single stone event). Renal colic treated with medication on Monday 12 November 2019 followed by stone passage without hematuria on Wednesday 13 December 2019 is considered two separate stone events (30 days between discrete event one and event two).

- Quality-of-life Questionnaires:

PedsQL

The PedsQL™ is a modular approach to measuring health related quality of life (HRQOL) in healthy children and adolescents and in those with acute and chronic health conditions. The multidimensional PedsQL Generic Core Scales were designed to measure the 3 core dimensions of health as delineated by the World Health Organization (WHO) in 1948 (physical, emotional, and social functioning), as well as role (school) functioning^{4,5,6}.

Questionnaires are administered to the participant and the participant's parent. The 23-item PedsQL™ is comprised of 5 items in the Emotional, Social and School Functioning dimensions (Psychosocial Health) and 8 items in the Physical Functioning (Physical Health) dimension. The questionnaire has specific versions for the child and the child's parent based on the age of the participant (5-7 years old, 8-12 years old, 13-18 years old). Questionnaires are administered based on the age of participant at baseline. The same version of the questionnaire will be used throughout the course of the study for a given participant based on age at baseline. Additionally, the family impact module is administered to the participant's parent.

Items are reverse-scored on a 0 to 4 Likert scale and linearly transformed to a 0 to 100 scale. Scale scores are computed as the sum of the items divided by the number of items answered (this accounts for missing data). If more than 50% of the items in the scale are missing, the scale score is not computed. Higher scores indicate better functioning and HRQOL. Further details and scoring instructions are provided in a separate document.

WPAI:PH, V2.0, CPV – Caregiver

Refer to details in Protocol Section 8.10.1.

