#### **4.4. End of Study Definition**

A participant is considered to have completed the study if he or she has completed all phases of the study, including the last visit or the last scheduled procedure shown in the Schedule of Activities (SoA), Section 1.3.

The end of the study is defined as completion of the last visit or procedure shown in the SoA in the trial globally.

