#### 8.3.1. Time Period and Frequency for Collecting AE and SAE Information

All SAEs will be collected from the signing of the ICF until 30 days after the last day of study participation.

All AEs will be collected from the signing of the ICF until the EOS/ET time point specified in the SoA (Section [1.3](#)).

All SAEs will be recorded and reported to the Sponsor or designee immediately and under no circumstance should this exceed 24 hours, as indicated in Section [10.3](#). The Investigator will submit any updated SAE data to the Sponsor within 24 hours of it being available.

Investigators are not obligated to actively seek AE or SAE after conclusion of the study participation. However, if the Investigator learns of any SAE, including a death, at any time after a participant has been discharged from the study, and he/she considers the event to be reasonably related to the study intervention or study participation, the Investigator must promptly notify the Sponsor.

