#### 9.4.3.2. Safety Endpoints

All safety analyses will be performed on the Safety Population. The incidence and nature of TEAEs and SAEs, along with change from Baseline in 12-lead ECG, physical examination findings, vital sign assessments, and clinical laboratory tests will be summarized.

Adverse events will be defined as treatment emergent if they have an onset or worsen in severity after a participant receives the study intervention. Treatment-emergent AEs will be summarized by SOC and preferred term according to the MedDRA. Treatment-emergent AEs will be further summarized by severity and relationship to study intervention. Adverse events leading to discontinuation, SAEs, and deaths will be summarized/listed.

Descriptive statistics will be provided for absolute values and changes from baseline in physical examination findings, vital sign measurements, ECGs, and clinical laboratory results at each timepoint.

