4.3.1.2 Secondary Endpoints in Safety

The secondary endpoints in safety are listed below:

- The incidence and nature of TEAEs and SAEs.
- Change from Baseline in 12-lead ECG, physical examination findings, vital sign assessments, and clinical laboratory tests.

All safety analyses will be performed on the SAF population and will be presented by PH type and by age group. All summaries will be descriptive in nature. No statistical comparisons will be performed.

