4.5.1 Other Significant Adverse Events

Adverse events of special interest (AESI) will be summarized and include injection site reactions, muscle pain or weakness, and kidney stone events.

An injection site reaction is a disorder characterized by an intense adverse reaction (usually immunologic) developing at the site of an injection. Potential ISRs will be graded as follows:

Individual signs or symptoms at the injection site (e.g., erythema, swelling, etc.) reported within 4 hours of study intervention administration will be recorded as AEs at injection site (not as an injection site reactions) and graded in accordance with the intensity categories.

At or after 4 hours post dose, signs or symptoms at the injection site will be evaluated according to the Common Terminology Criteria for Adverse Events (CTCAE; Version 5.0) criteria for injection site reactions.

Injection site reactions and treatment-emergent signs of muscle weakness or pain will be summarized by SOC and PT. Summaries for these events by maximum severity will also be produced. However, only summaries by maximum intensity for injection site reactions ≥ 4 hours post dose will be based on CTCAE grading criteria (Grades 1 through 5; where Grade 1 is least severe, and Grade 5 is most severe) for injection site reactions. If a participant has both missing and non-missing CTCAE grades for a given SOC and PT, the missing CTCAE grade is selected for reporting unless the non-missing CTCAE grades is noted as Grade 4 or Grade 5. Kidney stone events will be summarized by the specific kidney stone event type that is collected on the adverse event CRF: renal stone requiring medical intervention, stone passage with or without hematuria, and renal colic requiring medication. Kidney stone events will also be summarized by maximum severity.

By-participant data listings for injection site reactions, treatment-emergent signs of muscle weakness or pain, and treatment-emergent kidney stones will be provided.

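### The SAP's treatment-emergent definition is narrower than the protocol's at both ends, and its injection-site-reaction rule can hide a known Grade 1 to 3, with no departure declared

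*SAP*

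**What the plan says.** **Treatment-emergent definition.** Protocol 9.4.3.2: "Adverse events will be defined as treatment emergent if they have an onset or worsen in severity after a participant receives the study intervention". This has an onset limb and a worsening limb, and no end date. SAP 4.1.1.6 keeps only onset, from administration "of the first dose of study intervention and until the study completion date from the end of study CRF".

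**Collection periods.** Protocol 8.3.1: "All AEs will be collected from the signing of the ICF until the EOS/ET time point specified in the SoA". For serious events: "All SAEs will be collected from the signing of the ICF until 30 days after the last day of study participation". Protocol 4.4 describes a participant's completion as finishing all phases, "including the last visit or the last scheduled procedure shown in the Schedule of Activities (SoA), Section 1.3". The last scheduled visit is Day 180 (±5).

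**What is tabulated.** The SAP's secondary safety endpoint is "The incidence and nature of TEAEs and SAEs". Protocol 9.4.3.2 says: "Adverse events leading to discontinuation, SAEs, and deaths will be summarized/listed". Neither limits SAEs to treatment-emergent ones. In SAP 4.3.1.2.1, however, the overview rows for SAEs and deaths, and the SAE table by SOC and PT, are all limited to treatment-emergent events. SAP 4.1.1.7 puts all collected data in listings.

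**Injection site reactions (ISRs).** Where a participant has both graded and ungraded events in one SOC and PT, SAP 4.5.1 says "the missing CTCAE grade is selected for reporting unless the non-missing CTCAE grades is noted as Grade 4 or Grade 5".

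**Declared changes.** SAP 4.8 gives changes to protocol-planned analyses as not applicable.

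**The concern.** The SAP was meant to add detail to the protocol's analyses. Here it drops one limb of a definition, adds an end date, and lets an absent grade outrank a documented one. Each change can only move the summary tables towards fewer or milder harms, and none is declared.

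Safety is a secondary endpoint in children from birth to 11 years, with about 20 expected to complete, so a single event is visible in any table. The end date matters most for children who leave early, because exit can itself be prompted by safety. Protocol Appendix 6, for example, provides for children under 6 to leave the study when a qualifying transaminase elevation has no other explanation. At that point the treatment-emergent window closes while SAE collection continues.

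**Working it through.** The plan gives no figure to reproduce: there is no formal sample size calculation and no hypothesis test. The check is a comparison of rules plus date arithmetic.

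**1. Events with onset after exit**

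Inputs: Day 180 (±5) final visit and last dose at Day 150 (Protocol Schedule of Activities); 30-day SAE tail (Protocol 8.3.1). Assumption: the completion date on the end-of-study CRF is the day the participant exits.

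Share of post-first-dose SAE-collection days outside the window = 30 / (exit day + 30).

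| Exit day | Calculation | Share outside |
|---|---|---|
| 180 | 30/210 | 14.3% |
| 175 | 30/205 | 14.6% |
| 185 | 30/215 | 14.0% |
| 150 | 30/180 | 16.7% |
| 90 | 30/120 | 25.0% |
| 60 | 30/90 | 33.3% |
| 30 | 30/60 | 50.0% |

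SAE collection starts at consent. If a full 35-day screening period is added to the denominator, the completer's share is 30/245 = 12.2%; with the extra 14 days for repeat samples it is 30/259 = 11.6%.

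For a completer, the treatment-emergent window runs to 180 − 150 = 30 days after the last dose, and SAE collection to 210 − 150 = 60 days after it. The part left out is therefore about days 31 to 60 after the last dose.

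Effect of one lost participant among 20, with exact 95% intervals: 1/20 = 5.0% (0.1% to 24.9%) becomes 0/20 = 0% (0% to 16.8%).

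Expected number lost = 20 × rate × 30/365.25. The documents give no SAE rate for this period. Over an assumed range of 0.1 to 1.0 per patient-year the result is 0.16 to 1.64 events.

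**2. Worsening on drug**

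- AEs are recorded from consent, and screening can last 35 days (49 with repeat samples), so AEs can start before Day 1.
- Protocol 10.4.4.4 has updates entered on the existing eCRF record, so a worsening can keep its pre-dose onset date.
- SAP 4.1.1.7 confirms that onset governs: an AE in the year of first dose but an earlier month is not treated as potentially treatment-emergent.

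An AE that begins between consent and Day 1, worsens after dosing and is not entered as a new record is therefore treatment-emergent under the protocol and not under the SAP.

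**3. ISR maximum grade, when the same participant also has an ungraded event in that SOC and PT**

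| Highest known grade | Reported by SAP rule |
|---|---|
| 1 | missing |
| 2 | missing |
| 3 | missing |
| 4 | 4 |
| 5 | 5 |

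In Protocol Table 6, Grade 3 covers ulceration, necrosis and severe tissue damage.

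**The case against.** A reader might infer more than the text supports.

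- *Late SAEs disappear from the report.* They do not. All collected data are listed, and the general SOC/PT table in SAP 4.3.1.2.1 refers to participants with AEs and could be read as covering every AE. The protocol's own promise for SAEs and deaths allows summary or listing. The loss is from the tables named for SAEs and deaths.
- *All deaths in the 30 days after exit are dropped.* Treatment emergence follows onset. A death after exit from an event that began before exit still counts as a fatal TEAE.
- *Stopping drug closes the window.* In general it does not. Under Protocol 7.1.1, remaining visits continue after drug is stopped, so the early-exit shares apply only to children who leave the study.
- *All worsening is lost.* Protocol 10.4.1.1 makes exacerbation of a pre-existing condition an AE. Recorded after dosing, it has post-dose onset and is counted. The gap is limited to AEs that start between consent and Day 1 and are not entered as new records.
- *ISRs are under-counted.* The participant still counts as having an ISR; only the grade is obscured. Ungraded ISRs should be uncommon, because the protocol grades an event when it is recorded as an ISR, and in Study DCR-PHXC-201 all ISRs were Grade 1.

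The 30 post-exit days are also not equivalent to on-study days: no visit is scheduled in them, and investigators need not actively seek events once participation has ended. A plain 30-day extension has its own flaw, since completers may enter Study DCR-PHXC-301 at Day 180 and events under dosing there could be credited to this study.

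These points limit the size of the problem. They do not reconcile the two definitions or justify ranking a missing grade above a known one.

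**Conclusion.** The point holds in bounded form and should be fixed. The SAP's definition omits the protocol's worsening limb and closes before SAE collection ends. SAEs and fatal events with onset after exit miss every table named for them: 14% of post-first-dose collection days for a completer, rising to 50% for exit at Day 30. The ISR rule obscures known Grades 1 to 3 in mixed cases. The SAP declares none of the departures from the protocol.

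This rests on two readings of forms that are not in the documents: that the end-of-study CRF date is the exit date, and that a worsening AE is updated rather than re-entered. If the CRF date were set after the 30-day follow-up, the post-exit gap would close, but nothing in either document says so. The primary endpoint is untouched, and the study is descriptive and single-arm with full listings, so the matter does not threaten its main conclusion.

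**What to change.** 1. In SAP 4.1.1.6, restore worsening in severity after first dose to the TEAE definition. Confirm that the eCRF dates a severity change or requires a new record for it.
2. In SAP 4.3.1.2.1, tabulate all SAEs and deaths with onset from first dose through 30 days after last participation. Flag events after the first dose in Study DCR-PHXC-301, or attribute them to that study. State which date the end-of-study CRF supplies.
3. In SAP 4.5.1, report the highest non-missing ISR grade per participant and show ungraded ISRs in a separate row.
4. Record any remaining departure from the protocol in SAP 4.8.

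The cost is SAP wording, derivation code and table shells. The AE and SAE records are already collected; first-dose dates from Study DCR-PHXC-301 are needed for the attribution rule. The downside is that reported incidence or severity may rise slightly.
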